Patients will be randomly allocated to one of two groups, using random permuted blocks of 6. After eConsent collection, the investigator will enter the EDC portal and proceed with randomisation (also built into the EDC). Following randomisation, the investigator will contact the person responsible for the rehabilitation program in each group to allocate the participant to the respective study arm. Blinding of investigators and patients regarding allocation arm will not be possible, given the nature of the intervention. Analysis of study results will be performed by an independent statistician at UCSF.

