15. PARTICIPANT ASSESSMENTS

Patients will be assessed at baseline, 4 and 8 weeks.

Baseline Assessment

This assessment will involve a face-to-face visit, where the following information will be collected:

- a) date of birth
- b) gender
- c) height & weight
- d) body mass index
- e) formal education (years of schooling)
- f) job type
- g) previous shoulder surgery (> 3 months ago)
- h) Working status
- i) Geocodes/zip
- j) Race/ethnicity
- k) Age

The following outcomes will also be assessed in this visit: a) Shoulder Range of Motion; b) PROMIS CAT measures.

Shoulder Range of Motion will be measured in the following movements: 1) shoulder flexion; 2) shoulder abduction; 3) external rotations with shoulder abducted at 90 degrees. The participant will be asked to perform three non-painful repetitions of each movement, in a standing position. The investigator will measure the maximum joint angle attained by the participant, using a digital goniometer in each repetitions. The highest of the three values will be considered.

Regarding satisfaction with social role and ability to participate in social roles and activities, these will be collected through PROMIS CAT v2.0. These will be collected onsite, and the results will then be transferred by the investigator to the eCRF.

Assessment of primary outcome, as well as the remaining secondary outcomes will be performed through an electronic questionnaire to be filled by participants, through the EDC system. These will need to be filled within 5 consecutive days, counting from the date they are sent to the participant. To promote compliance with this schedule, whenever the deadline is approaching, automatic email reminders will be sent to participants. Participants will be excluded from the study

for protocol breach in case they don't fill in the assessment forms. Upon completion of the baseline form, participants in the study will receive a stipend of \$25.

Additional measurements of upper limb function and tri-dimensional motion will also be performed at the onsite visit by the clinician, using a motion capture system. These will not be considered in the outcomes of this study, but will be made available for post-hoc analysis.

Interim assessment (4 weeks)

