Participants will be required to complete a questionnaire similar to the baseline assessment, within a 5-day window beginning at the start of week 4. These assessments will include all the information pertaining to the primary and secondary outcomes, except for those that are collected through a face-to-face assessment. These (shoulder range of motion and PROMIS CAT measures) will not be collected on this assessment. Upon completion of this form, participants in the study will receive a stipend of \$25.

Final assessment (8 weeks)

This assessment will involve a face-to-face visit, where the following outcomes will be assessed: a) shoulder Range of Motion; b) PROMIS CAT measures and c) Participant satisfaction (Net Promoter Score). Shoulder Range of Motion and PROMIS CAT measures will be assessed using a similar methodology to the one descried for the baseline assessment.

Participants will also be required to complete a questionnaire similar to the baseline and interim assessments, within a 5-day window beginning at the start of week 4. These assessments will include all the information pertaining to the primary and secondary outcomes, except for those that are collected in the face-to-face visit. Upon completion of this form, participants in the study will receive a stipend of \$25.

Additional measurements of upper limb function and tri-dimensional motion will also be performed at the onsite visit by the clinician, using a motion capture system. These will not be considered in the outcomes of this study, but will be made available for post-hoc analysis.

Engagement assessment

For participants on the digital group, engagement and usage metrics of the educational and CBT components will also be collected automatically.

Additionally, the following activity log will be collected from patient's Electronic medical records and time stamps, as well as paper survey (or, in the case of the digital group, sent to the study coordinator via email, with the participant identified only by the study ID), to be entered into EDC portal by study coordinator:

- 1. Face-to-face visits registry (dates, times and duration)
- 2. Remote sessions registry (dates, times and duration)
- 3. Number and duration of contacts between PT and participant (emails, text messages, phone and videocalls)
- 4. Total time spent on remote monitoring of the patient (digital group only)

Adverse events

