ANNEX 3- CONVENTIONAL PT INTERVENTION PROTOCOL

The co-investigators are encouraged to use the McClure's staged based rehabilitation therapy (STAR) classification (see Table 1) as a *guide* but not necessarily as a prescriptive manner to select interventions. Instead, the co-investigators will reference their use interventions categorized based on commonly practiced in an outpatient physical therapy setting (see Table 2).

McClure's stage-based rehabilitation therapy (STAR) intervention approach is based on the Irritability of the patient's condition. Assessments of symptoms of Irritability are gathered from the patient's history and findings from the examination. Table 1 represents a guided approach to STAR for the chronic shoulder pain population and the type of interventions used. Table 2 describes the type of commonly used physical therapy interventions that could be used in the cohorts.

Guideline to help determine the stage of Irritability is based on both history and examination findings*

High	Moderate	Low
• Pain >= 7/10	• Pain (4-6/10)	• Pain (<= 3/10)
• Consistent night or	• Intermittent night or rest pain	• Absent night or rest pain
resting pain	• Pain at end of range	• Minimal pain with overhead
• Pain before end of range	• AROM and PROM close	• AROM = PROM
• AROM < PROM	• Moderate disability	• Low disability
• High disability		
Approach: Minimize	Approach: Mild-moderate physical	Approach: Mod-high physical
physical stress	stress	stress
• Activity	Basic-level functional	• High-demand functional
modification	activity restoration	activities

*Taken from Staged approach (STAR) for rehabilitation classification by McClure et al.

Table 1. McClure's staged approach to shoulder intervention based on different impairments

Impairments	Irritability	Intervention	Examples of
		Approaches	Intervention**
Restricted passive mobility	Low	• ROM	• Aggressive active and
due to joint/muscle/neural		• Stretching	passive stretches (e.g.,
tissues		• manual therapy:	sleeper stretches;
		tolerable stretch	foam roller T's, Y's,
		sensation at end-	I's; Doorway stretch)
		range	
		Hold longer	
		duration and	
		frequency	
Restricted passive mobility	Moderate	• ROM	• Active and passive
due to joint/muscle/neural		• Stretching	stretches (e.g., gentle
tissues		• Comfortable end-	sleeper stretches;
		range manual	Foam roller T's, Y's,
		therapy	I's; modified to $\frac{1}{2}$ to
			full foam roller T's,
			Y's, I's; Modified
			doorway stretch)

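### The week-8 satisfaction score is taken only at the clinic visit, at the site that delivers conventional PT, so courtesy answers can differ by arm; the electronic questionnaire is the better place for it.

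*Combined protocol and SAP*

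**What the plan says.** Section 8.2 lists patient satisfaction, a 0 to 10 Net Promoter Score question about the programme, as a secondary outcome, and shoulder range of motion as another. Section 16 compares the interventions on such outcomes at a significance level of 0.05.

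Under the final assessment, Section 15 gives the content of the face-to-face visit as "a) shoulder Range of Motion; b) PROMIS CAT measures and c) Participant satisfaction (Net Promoter Score"). The 8-week electronic questionnaire covers the primary and secondary outcomes except those taken at the visit.

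For range of motion, the baseline text of Section 15 says "The investigator will measure the maximum joint angle attained by the participant, using a digital goniometer in each repetitions", and "The highest of the three values will be considered". For week 8 it says "Shoulder Range of Motion and PROMIS CAT measures will be assessed using a similar methodology to the one descried for the baseline assessment".

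On masking, Section 13 states "Blinding of investigators and patients regarding allocation arm will not be possible, given the nature of the intervention". Its one independence safeguard concerns analysis: "Analysis of study results will be performed by an independent statistician at UCSF".

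On delivery, Section 14 has the sponsor assign a physical therapist to each digital participant. Conventional PT is given face to face in an outpatient clinic by therapists who use the UCSF messaging system. Annex 3, on choosing the conventional interventions, begins "The co-investigators are encouraged to use" and goes on to name a staged classification as a guide.

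**The concern.** Any open-label trial carries some response bias. The difficulty here is that the place of collection is tied to one arm only. A participant in conventional PT is asked at the treating clinic whether they would recommend what that clinic provided. A digital participant is asked at the same clinic about a programme supplied by someone else. If politeness towards the clinic raises scores, it need not raise them equally, and an unequal effect does not cancel in the comparison between arms.

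The same section has all participants assessed at the final appointment to decide whether they need further care, arranged with a UCSF physical therapist. If that appointment is the 8-week visit, as it appears to be, some participants rate their programme while the clinic considers their continuing care.

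At stake is the interpretability of the satisfaction comparison. Range of motion raises a separate and weaker question of observer expectation.

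**Working it through.** No figure in the plan bears directly on this point, so the check is mainly a comparison of passages.

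**Step 1. Mode of collection at week 8.** Section 8.2 has ten secondary outcomes, (a) to (j).

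| Outcome | Where collected at week 8 |
|---|---|
| QuickDASH (primary) | EDC, self-completed |
| (b) to (g): pain, surgery interest, medication, fear avoidance, anxiety and depression, work productivity | EDC, self-completed |
| (a) range of motion | site visit, goniometer |
| (h) PROMIS CAT | site visit |
| (i) engagement | usage data and activity logs |
| (j) satisfaction | site visit |

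Six of the ten are self-completed electronically (10 − 3 on site − 1 from logs = 6). Satisfaction is a single question that needs no instrument. At week 4, Section 15 names only range of motion and PROMIS CAT as exceptions to the electronic form. Read literally, satisfaction is electronic at week 4 and moves to the visit at week 8. No reason is given.

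**Step 2. Who delivers each arm.** Sections 14a and 14b together with Annex 3 tie the site to conventional PT and the sponsor's therapists to the digital programme.

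**Step 3. Who asks.** Section 8.2 says only that participants are asked. Section 15 does not name the person or say whether the item is spoken or written.

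**Step 4. Effect on the comparison.** Let courtesy raise the mean score by c₁ in the conventional arm and c₂ in the digital arm. The observed difference, conventional minus digital, is the true difference plus (c₁ − c₂). It is unbiased only if c₁ = c₂. The documents give neither value, nor an SD for the score.

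**Step 5. Illustration on assumed values only.** Let the true difference be 0 and the net shift be b standard deviations, with n per arm. The chance that a two-sided 0.05 test rejects is approximately Φ(b/√(2/n) − 1.96) + Φ(−b/√(2/n) − 1.96). Take n = 40 as planned in Section 9, and n = 40 × 0.90 = 36 after its 10% dropout.

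| Assumed b | n = 36 | n = 40 |
|---|---|---|
| 0 | 5.0% | 5.0% |
| 0.1 | 7.1% | 7.3% |
| 0.2 | 13.6% | 14.5% |
| 0.3 | 24.7% | 26.9% |
| 0.5 | 56.4% | 60.9% |

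Example: for n = 40 and b = 0.2, √(2/40) = 0.224 and 0.2/0.224 = 0.894, so Φ(−1.066) + Φ(−2.854) ≈ 0.143 + 0.002 = 0.145. This shows sensitivity; it does not estimate the bias in this trial.

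**Step 6. Range of motion.** The reader is an investigator, investigators are not blinded, and the week-8 method follows baseline. Section 13 refers to investigators and patients and does not treat the outcome assessor as a separate role. Nothing in the documents indicates which way an unblinded reading would lean.

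**The case against.** The strongest reply is that the link between assessor and control arm is thinner than it looks. A reader might infer that control participants rate their programme in front of the therapist who treated them. The documents do not say so: nobody is named as taking the score, and no treating therapist is placed at the visit. Nor is it settled that investigators treat. Annex 3 suggests that co-investigators do, but other sections keep the roles apart. In Section 13 the investigator contacts the person responsible for each group's rehabilitation. In Section 14b the physical therapist adapts the programme. In Section 15 the primary investigator coordinates with a UCSF physical therapist. In Section 17 therapists report adverse events to the investigators. This objection stands, and it limits the point to the setting: the score is collected at a site that delivers one arm.

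A reader might also infer that range of motion is biased towards conventional PT. That is not supported. The study hypothesis is that the digital programme does at least as well, so expectation could push the reading either way.

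A third tempting inference is that moving the item would yield more satisfaction data. Some who miss the visit may complete the form, but others may attend and miss the form's 5-day window. The net effect cannot be determined.

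It is also fair to say that the lack of blinding is openly disclosed and that the primary outcome is not collected at the visit. Neither removes the differential risk to the satisfaction score, and an independent statistician cannot correct how an answer was obtained.

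**Conclusion.** The point holds as a minor design improvement. Collecting satisfaction only at the site that provides conventional PT creates a risk of courtesy answers that differ by arm, and nothing in the plan offsets it. The conclusion rests on two readings: that the outpatient clinic delivering conventional PT is the study site, which Sections 11 and 14b and Annex 3 support; and that some participants answer more favourably at a clinic visit than on a private form, which is an assumption. If courtesy favours the treating clinic, the shift would be towards conventional PT, but the documents fix neither its direction nor its size.

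The range-of-motion point is secondary: an unblinded reading can be biased, in an unknown direction. The primary QuickDASH comparison does not depend on either measurement.

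**What to change.** 1. In Section 15, remove the Net Promoter Score from the 8-week face-to-face visit and add it to the 8-week EDC questionnaire for self-completion. First reconcile that questionnaire's window, which is stated as opening at the start of week 4, with the 8-week time point. The cost is one item on an existing form. The small downside is that a participant who attends the visit but does not complete the form in its 5-day window has no score; that participant would also lack the week-8 QuickDASH.

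2. State who reads the goniometer at week 8. Where existing staffing allows, use a co-investigator who neither treated nor randomised that participant, and take the reading before any discussion of care. The documents refer to more than one co-investigator but give no number, so it cannot be assumed that this needs no extra staff, and some participants will reveal their arm. If it is not practicable, report the unblinded reading as a limitation.

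Neither change alters the sample size, the tests or the treatment, and the first can be made without the second.

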8. STUDY OUTCOMES

8.1 Primary Outcome

Impact on physical function and symptoms measured through the shortened Disabilities of the Arm, Shoulder and Hand questionnaire (QuickDASH) between baseline and 8 weeks.

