The CBT program will take the form of a self-paced program consisting of written and prerecorded audio materials. An email will be sent weekly by the physical therapist to the participant, during the 8 weeks of the program. Each email will contain an introductory text describing the objectives for that week, as well as a link to that week's audio session and a PDF attachment with self-guided exercises. The CBT component is not mandatory per protocol, but metrics on user engagement will be measured.

b. Conventional PT

Patients in this group will benefit from a 8-week program consisting of two 30 min face-to-face PT sessions per week in an outpatient clinic setting, for a total of 16 sessions. The program will follow the principles outlined in **Annex 3**, which includes commonly used interventions adapted by the physical therapist to the specific needs of the participant.

Participants in this group will be excluded from the per protocol analysis if they complete less than 14 sessions over 8 weeks. Participants in this group will be considered as dropouts if they: a) choose to abandon the study; b) miss four consecutive scheduled PT sessions.

In addition to the face-to-face sessions, PTs will also be communicating with participants in this group through a secure messaging system (Mychart) used at UCSF or, alternatively, through a telephone check-ins (10-15 min calls, up to twice per week).

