16. STATISTICAL ANALYSIS PLAN

To assess differences in clinical and demographic variables of the patients allocated to the two study groups, independent samples t test or Mann–Whitney U test will be used for quantitative variables. For categorical variables, Chi-square test or Fisher's exact test will be used. Outcome analysis will be performed using both an intention to treat analysis and a per-protocol analysis.

The overall impact of the intervention on the primary and secondary outcomes will be assessed considering both the results at the 8-week assessment as well as change from baseline.

Differences between interventions will be evaluated using independent samples t test or Mann-Whitney U test. For non-normally distributed variables, the magnitude of the difference in the medians will be assessed using Hodges-Lehman estimator. Additionally, a repeated measures ANOVA will also be performed, with group as an independent factor and time as a within-subjects factor. When necessary, logarithmic transformation will be performed to obtain normally distributed variables. In all analysis, a significant level of 0.05 will be considered.

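### The 8-week questionnaire that carries QuickDASH is given the week-4 window, contradicting the 8-week primary endpoint

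*Combined protocol and SAP*

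**What the plan says.** Section 8.1 defines the primary outcome through the "shortened Disabilities of the Arm, Shoulder and Hand questionnaire (QuickDASH) between baseline and 8 weeks". Section 15 opens with the schedule: "Patients will be assessed at baseline, 4 and 8 weeks". Its baseline part says how the primary outcome is captured: "Assessment of primary outcome, as well as the remaining secondary outcomes will be performed through an electronic questionnaire".

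The two follow-up paragraphs of Section 15 then give the windows:

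- Interim assessment (4 weeks): a "questionnaire similar to the baseline assessment, within a 5-day window beginning at the start of week 4".
- Final assessment (8 weeks): a questionnaire "similar to the baseline and interim assessments, within a 5-day window beginning at the start of week 4".

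The final paragraph also describes an in-person appointment, "where the following outcomes will be assessed: a) shoulder Range of Motion; b) PROMIS CAT measures and c) Participant satisfaction (Net Promoter Score"). QuickDASH is not on that list. The final questionnaire takes every primary and secondary outcome that the visit does not, so it carries QuickDASH.

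Section 16 analyses the outcomes "considering both the results at the 8-week assessment as well as change from baseline".

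**The concern.** The final form has the same window as the interim form, although its heading and the rest of the document place it at 8 weeks. This is the primary outcome's collection instrument, and the sentence is the only place that says when its final administration opens.

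If the EDC system or site staff followed the sentence, two near-identical forms would be due in the same five days around week 4. The trial would then hold no QuickDASH value at 8 weeks. The 8-week comparison, the change from baseline and the last time point of the repeated measures ANOVA in Section 16 would have no data. A missed 8-week questionnaire cannot be recovered afterwards. Section 15 also ties automatic reminders, and exclusion for non-completion, to these forms, so their timing has practical consequences.

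**Working it through.** **1. The statements side by side**

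| Place | Time point for the final QuickDASH |
|---|---|
| Section 8.1 | 8 weeks |
| Section 15, opening schedule | 8 weeks |
| Section 15, heading of the final assessment | 8 weeks |
| Section 16 | 8 weeks |
| Section 15, sentence giving the final window | start of week 4 |

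Four places agree and the one that sets the window does not. Two other texts might be thought to settle the matter, but neither does. The five-day completion rule in the baseline part of Section 15 runs from the date the form is sent and gives no send date. The 8-week remote assessment in Annex 2 belongs to the digital exercise protocol only and does not mention QuickDASH.

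**2. Day counts**

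Convention: the first day of week 1 is day 1, and weeks are numbered from 1 as Annex 2 does. Week k then opens on day 7(k − 1) + 1.

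- Week 4 opens on day 7 × 3 + 1 = 22; the five-day window is days 22 to 26. Completed by then: 21 of 56 days, 21/56 = 37.5%.
- Week 5, where Annex 2 Phase 2 begins, opens on day 7 × 4 + 1 = 29. The written window has closed by then.
- Week 8 opens on day 7 × 7 + 1 = 50; window 50 to 54.
- The first day after 8 completed weeks is 56 + 1 = 57; window 57 to 61.
- Gaps: 50 − 22 = 28 days to the start of week 8; 57 − 22 = 35 days to the end of 8 completed weeks.

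**3. Treatment scheduled by then, conventional arm**

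Section 14 gives "two 30 min face-to-face PT sessions per week in an outpatient clinic setting, for a total of 16 sessions". Assuming the program starts on day 1 and sessions are held as scheduled:

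- before day 22: 3 × 2 = 6 of 16;
- before day 50: 7 × 2 = 14 of 16;
- before day 57: 8 × 2 = 16 of 16.

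**4. Sensitivity to the counting rule**

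If week 4 is instead read as 4 completed weeks, the written window opens on day 28 + 1 = 29, at 28/56 = 50% of the program and with 4 × 2 = 8 of 16 conventional sessions scheduled. The matching 8-week opening is day 57, and 57 − 29 = 28 days. Under either rule the final window coincides with the interim window and opens 28 days before its week-8 counterpart. Calling the first day day 0 shifts every label by one and changes no difference.

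**5. What replacing 4 with 8 alone would leave open**

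The form would open on day 50 or day 57, depending on the reading: 7 days apart, with 14 or 16 of the 16 conventional sessions scheduled. On the first reading the last program week is still to come.

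**The case against.** The strongest reply is that nobody would be misled. The heading, the schedule, the endpoint definition and the analysis section all say 8 weeks, and nothing supports a week-4 final form. The faulty sentence itself describes a form distinct from the interim one, with its own stipend, so the literal reading defeats itself. Nothing in the document shows that the EDC has been set up wrongly. On this view it is a one-word typographical error of low severity.

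Much of that stands: the intent is recoverable and the harm depends on someone following the sentence. It does not make the sentence right. People who build and run an assessment schedule work from the assessment section, and this is the only window it gives for the final primary-outcome form.

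A second reply is that some figures depend on how weeks are counted. That is true of days 22 to 26, 37.5%, 6 of 16 sessions and closure before Phase 2. The week numbering behind them comes from Annex 2, which covers only the digital arm. The 35-day figure compares the start of a numbered week with the end of 8 completed weeks; like for like, the gap is 28 days. The overlap with the interim window and the 28-day gap do not depend on the convention.

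Thirdly, the choice between the start of week 8 and 8 completed weeks concerns replacement wording that is not in the protocol, and the documents state no delay in starting treatment. That is fair. It is a clarification to make in the same edit and adds nothing to the severity.

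**Conclusion.** The concern holds. The window for the final questionnaire is wrong as written and conflicts with four other statements of the 8-week time point. Because that questionnaire carries QuickDASH, the error sits on the primary endpoint: applied literally, it yields two QuickDASH forms in one five-day window and none at 8 weeks. The written window opens 28 days before the corresponding week-8 window under either way of counting weeks. The session counts assume that treatment starts on day 1 and runs to schedule; the documents give no start delay.

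It is very probably a copy of the interim wording. Design, analysis and sample size are unaffected. It must still be fixed, because it is an operative instruction for the primary outcome.

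**What to change.** In the final-assessment paragraph of Section 15, replace the week-4 window with one at the 8-week time point, and check that the schedule programmed in the EDC matches.

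In the same edit, as a clarification, state whether the form opens at the start of week 8 or after 8 completed weeks, counted from one stated origin that is the same in both arms. Section 8.1 implies baseline as that origin. Apply the same counting rule to the interim window.

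The cost is one corrected sentence, a short counting rule and an EDC check. No visits or patients are added.
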